7 RANDOMIZATION AND TREATMENT ASSIGNMENT

Subjects will be randomized at a 2:1 allocation to receive 8 mg/kg AMG 714 or placebo for a total of 7 administrations over 10 weeks.

Randomization and initial dosing of the first ten (10) subjects will be staggered to allow observation in the initial subjects for any possible unanticipated side effect in the RCD-II population. To this effect, the first dosing of the first ten subjects will adhere to the following rules:

- No more than one subject per day.
- No more than two subjects per week.
- These rules will be implemented via randomization. The sites will obtain written approval from the Sponsor before dosing subjects by means of a Randomization Approval Form.

8 DURATION OF STUDY

Screening Visit: Up to 4 weeks (28 days)

Double-blind randomized period: 12 weeks

Final Visit: 4 weeks after last double-blind randomization visit

Duration of study per subject: Up to 20 weeks

Duration of entire study: Approximately 1.5 years

9 SUBJECT POPULATION

Approximately 24 males and females 18 years of age or older will be randomized into the study. Non-evaluable subjects will be replaced, if possible, at the discretion of the Sponsor.

Subjects will undergo screening procedures within 28 days of Visit 1; Week 0/Day 0. Those subjects who meet the study entry criteria will be invited to participate in the study.

9.1 INCLUSION CRITERIA

Subjects must fulfill all of the following inclusion criteria to be eligible for participation at screening and at Visit 1; Week 0/Day 0:

1. Adult males or females, 18 years of age or older.
2. Demonstrated willingness to participate in the study as documented by signed informed consent.
3. Females of non-childbearing potential defined as postmenopausal (>45 years of age with amenorrhea for at least 12 months or any age with amenorrhea for at least 6 months and a serum follicle stimulating hormone [FSH] level >40 IU/L at Screening); or permanently sterilized (e.g., bilateral tubal occlusion, hysterectomy, bilateral salpingectomy, oophorectomy); or otherwise incapable of pregnancy

OR

Females of child bearing potential (FOCBP) or males who agree to practice two highly effective methods of birth control (as determined by the Investigator; one of the methods must be a barrier technique) from Screening through the end of study participation (Visit 9, Week 16/Day 112).

4. Prior confirmed diagnosis of RCD-II defined by the following criteria: celiac disease confirmed by histology, endoscopy or serology; with persistent and recurrent symptoms (e.g., diarrhea, weight loss, abdominal pain); with abnormal small bowel histology; with aberrant intraepithelial lymphocytosis of > 20% aberrant IELs vs total IELs (as determined by flow cytometry (or >50% if determined by immunohistochemistry); despite adherence to a strict GFD for at least 6 months and after exclusion of other potential causes of symptomatic non-response (e.g., microscopic colitis, bacterial overgrowth, lactose intolerance, exocrine pancreatic insufficiency, hyperthyroidism, etc.) and intestinal histological abnormality (autoimmune enteropathy, giardiasis, immunodeficiency, collagenous sprue, Whipple's disease, etc.).

NOTE: Subjects who have been treated for RCD-II must continue to have increased aberrant IELs (>20% vs total IELs vs total IEL by flow cytometry or >50% by IHC) and abnormal small bowel histology (Marsh \geq 1) and must have had prior history of symptoms; however, symptoms are not required of previously treated subjects, or subjects being treated with steroids, at the time of study entry.

5. Total attempted adherence to a GFD for at least 6 consecutive months prior to screening. Subjects must also agree to make no changes to their current GFD for the duration of study participation.
6. Anti-tissue transglutaminase (IgA and IgG) at screening <2 x the diagnostic level for celiac disease (weak positive or negative).
7. HLA-DQ typing compatible with celiac disease, provided or obtained prior to baseline biopsy.

8. Life expectancy > 4 months.
9. Laboratory values:
 - a) Estimated CCr > 30 mL/min/1.73m² using the Cockcroft-Gault equation
 - b) Serum AP, ALT/SGPT, and AST/SGOT less than 3x the ULN
 - c) Total bilirubin of less than 2.5 x ULN
 - d) Total WBC > 300/mm³
 - e) Platelet count > 85,000/mm³
 - f) INR less than 1.5
 - g) Albumin of more than 10 g/L (i.e., 1 g/dL or 1.45 μmol/L)
10. Subjects receiving systemic steroids must be on a stable dose for at least 4 weeks prior to randomization; the dose should not exceed 20 mg of prednisone, prednisolone or equivalent per day. Oral budesonide will be accepted at a maximum dose of 9 mg per day.
11. Willingness and ability to comply with study procedures and protocol stipulated concomitant medication guidelines.
12. Willingness to return for all scheduled follow-up visits.

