	
participation and follow-up in the clinical trial or put the subject at unnecessary risk including but not limited to:
 
 a) Cardiovascular disease [e.g., uncontrolled hypertension (defined as office systolic blood pressure [BP] equal to or greater than 180 mmHg or office diastolic BP equal to or greater than 110 mm/Hg), unstable angina, congestive heart failure worse than the New York Heart Association Class II, coronary angioplasty or myocardial infarction within the last 6 months, uncontrolled atrial or ventricular cardiac arrhythmias clinically significant pleural or pericardial effusion or ascites) b) pulmonary disease (e.g., severe chronic pulmonary disease) c) renal, hematological, gastrointestinal, endocrine (e.g., poorly controlled diabetes), immunologic, dermatologic, neurological, or psychiatric disease 
 5. History of significant immune suppression: 
 - Bone marrow transplant (BMT) or cladribine therapy less than 6 months prior to baseline. In other words, cladribine and bone marrow transplant naïve, primary non-responders (treatment resistant), secondary non-responders (relapse after response/remission) and incomplete responders may be enrolled in the study if cladribine therapy and/or BMT were not provided within the 6 months prior to randomization. - Potent systemic immune suppressants (e.g., azathioprine) in the 3 months prior to baseline. 6. History of alcohol or drug abuse that would interfere with the ability to comply with the study protocol. 7. History of clinically significant hypersensitivity to the study drug or any related drugs or to any of the excipients. 8. Positive hepatitis B (Hep B), hepatitis C (Hep C), or Human immunodeficiency virus (HIV) infection test results at the time of screening. 9. Females who are pregnant or are planning to become pregnant during the study participation period or 6 months after last dose, or are currently breastfeeding.
--	---

	
10. Participation in another investigational drug or device study or treatment with an investigational drug within 30 days or 5 half-lives, whichever is longer, prior to randomization.
 
11. Any additional reason, which in the opinion of the Investigator, would prevent the subject from safely participating in the study or complying with protocol requirements.

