1.6 EFFECTS OF AMG 714 IN HUMANS

The original hybridoma-derived material produced by Genmab (AMG 714-HYB) was evaluated in subjects with RA in a Phase 1 study (Hx-IL15-001) and a Phase 2 study (20030210). [REDACTED] AMG 714 is now produced by a CHO cell line. [REDACTED]

[REDACTED] AMG 714-CHO was studied in a first-in-human trial to investigate safety, tolerability, pharmacokinetics, and pharmacodynamics in healthy subjects (Phase 1 Study 20050193) and in a proof-of-concept study in patients with psoriasis (Phase 2 Study 20060349). To date, AMG 714 has been shown to have clinical effect in RA; tolerability comparable to placebo in ~200 subjects exposed (including ~140 exposed for 12 weeks of bi-weekly dosing); a favorable pharmacokinetic profile with 3 weeks half-life; and no significant immunogenicity signal.

All completed clinical studies of AMG 714-CHO and AMG 714-HYB are summarized in Table 3.

Table 3. Summary of AMG 714 Clinical Studies

Study Number (Phase)	Key Design Features	Dose Route, Duration	Study Population	Status
AMG 714-CHO				
20050193 (Phase 1; Amgen)	Double-blind, placebo-controlled, single SC or IV doses, dose-escalation study	SC doses: 0, 30, 100, 300 or 700 mg (cohorts 1 to 4) IV dose: 0 or 100mg IV infusion (cohort 5) ^d Single dose	40 healthy subjects	Completed
20060349 (Phase 1b/2a; Amgen)	Double-blind, placebo-controlled, multiple SC doses, dose-escalating study	0 or 150 mg SC (cohort 1) 0 or 300 mg SC (cohort 2) Dose every 2 weeks for 12 weeks	22 subjects with moderate to severe psoriasis	Completed ^b
AMG 714-HYB				
Hx-IL15-001 (Phase 1; Genmab)	Double-blind, placebo-controlled, single SC infusion, dose escalation, study with open-label, repeat-dose (4 weekly doses) follow-up	Initial single dose: 0 or 0.15 to 8 mg/kg SC infusion Repeated dose: 0.5 to 4 mg/kg SC infusion once weekly for 4 weeks 5 doses total over 8 weeks	30 subjects with RA ^c	Completed
20030210 ^d (Phase 2; Genmab/Amgen)	Double-blind, placebo-controlled, multiple SC infusion, parallel-group, multicenter study	0 or 40 to 280 mg SC infusion dose every 2 weeks for 12 weeks with initial 200% loading dose	180 subjects with RA	Completed

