Subjects will be expected to maintain total adherence to a GFD from 6 months before randomization through the final study visit (Visit 9; Week 16/Day 112). Subject's adherence to the GFD will be assessed by an expert dietitian and monitored via stool sample testing using the iVYLISA GIP stool gluten test. Subjects with known or suspected GFD transgressions will be counseled and allowed to continue in the study.

A study site staff member will contact each subject by telephone one day after the first study drug administration to assess for AEs. Subjects will return to the clinic for the next administration of study drug after 1 week (Visit 2; Week 1/Day 7). After Visit 2, subjects will return to the clinic for follow-up and study drug administration at Visit 3 (Week 2/Day 14) and

[figure not shown]
every two weeks thereafter as indicated in the study schedule of events (Table 1). The final dose of study drug will be administered at Visit 7 (Week 10/Day 70). An end-of-study efficacy visit will be conducted at Visit 8 (Week 12/Day 84). The final study visit will be conducted 6 weeks after the last dose of study drug at Visit 9 (Week 16/Day 112).

Subjects who meet all other study entry criteria will undergo upper gastrointestinal endoscopy with biopsy collection prior to baseline (i.e., prior to Visit 1, Week 0/Day 0) and within 7 days of Visit 8 (Week 12/Day 84) in order to assess changes from baseline to end of treatment in aberrant and abnormal IELs, VH:CD ratio, TcR clonality and Marsh score.

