 7. History of clinically significant hypersensitivity to the study drug or any related drugs or to any of the excipients.
 8. Positive Hep B, Hep C, or HIV test results at the time of screening.
 9. Females who are pregnant or planning to become pregnant during the study participation period of 6 months after last dose, or are currently breastfeeding.
 10. Participation in another investigational drug or device study or treatment with an investigational drug within 30 days or 5 half-lives, whichever is longer, prior to randomization.
 11. Any additional reason, which in the opinion of the Investigator, would prevent the subject from safely participating in the study or complying with protocol requirements.

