21.6.3 Pregnancy

Any pregnancy that occurs during the study or within 6 months of the last dose of study drug should be recorded on a Pregnancy Report Form to facilitate outcome follow-up. Pregnancy should be reported whether occurring in a female subject or the partner of a male subject. Spontaneous abortion should be reported as an SAE.

Regardless of subject sex, the Investigator should counsel the subject (and partner, if appropriate) regarding possible effects on the fetus and risks of continuing with the pregnancy. Monitoring should continue until conclusion of the pregnancy.

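### Inclusion criterion 3 ends contraception 6 weeks (about two stated half-lives) after the last dose, some 20 weeks before the protocol's own 6-month pregnancy windows close

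*Protocol*

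**What the plan says.** - **Contraception.** Inclusion criterion 3, in the synopsis and in Section 9.1, requires two highly effective methods "from Screening through the end of study participation (Visit 9, Week 16/Day 112". It covers females of childbearing potential and males.
- **Timing.** Section 6 puts the last dose at Week 10/Day 70 and adds: "The final study visit will be conducted 6 weeks after the last dose of study drug at Visit 9 (Week 16/Day 112".
- **Planned pregnancy.** Exclusion criterion 9 applies to females only. The synopsis excludes those "planning to become pregnant during the study participation period or 6 months after last dose"; Section 9.2 has "planning to become pregnant during the study participation period of 6 months after last dose". The 'of' in Section 9.2 is evidently a slip for 'or', and both versions end at 6 months.
- **Pregnancy reporting.** Section 21.6.3 covers "Any pregnancy that occurs during the study or within 6 months of the last dose of study drug" and continues: "Pregnancy should be reported whether occurring in a female subject or the partner of a male subject".
- **Washout of other drugs.** Exclusion criterion 10 rules out another investigational drug "within 30 days or 5 half-lives, whichever is longer, prior to randomization".
- **Half-life.** Section 1.6 describes "a favorable pharmacokinetic profile with 3 weeks half-life".

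The text available contains no instruction to continue contraception after Visit 9. Scheduled pregnancy testing in Table 1 also ends at that visit.

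**The concern.** The protocol treats pregnancy as relevant for 6 months after the last dose when it screens for intention and when it collects reports, but the measure that prevents pregnancy lapses at 6 weeks. A participant who follows the plan exactly may stop contraception at Visit 9 while a meaningful amount of a long-lived antibody is probably still circulating.

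The other two rules do not fill the interval. Exclusion criterion 9 screens intention at entry, in women only. It leaves unplanned pregnancy and a later change of mind uncovered, and it does not reach men. Section 21.6.3 records a pregnancy after it has happened. For male subjects nothing preventive applies after Week 16, although a partner's pregnancy stays reportable for about 20 more weeks. The stake is participant and fetal safety; the efficacy analysis is unaffected.

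**Working it through.** **Inputs**

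| Quantity | Value | Source |
|---|---|---|
| Last dose | Day 70 | Protocol 6 |
| End of contraception | Day 112, ±7 days | Protocol 9.1; window from Protocol 11 |
| Half-life | 3 weeks = 21 days | Protocol 1.6 |
| Pregnancy windows | 6 months after last dose | Exclusion 9; Protocol 21.6.3 |
| Predicted serum levels | always above 59 µg/mL; above 96 µg/mL following the Week 1 dose | Protocol 18.3 |
| Possible protein loss | up to 40% | Protocol 18.3 |
| Concentration treated as active | 10 µg/mL | Ex vivo work in Protocol 18.3; minimum exposure target in SAP 4 |

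**1. The protocol's own interval.** 112 − 70 = 42 days = 6 weeks, which agrees with Section 6. In half-lives, 42/21 = 2.0.

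**2. Gap to the 6-month windows.** Taking 6 months as 26 weeks, 26 − 6 = 20 weeks. By calendar, 365.25/2 = 182.6 days, so the windows close at Day 252.6 and the gap is (252.6 − 112)/7 = 20.1 weeks. Across the ±7-day Visit 9 window it is 19.1 to 21.1 weeks. With 6 months taken as 180 days it is 19.7 weeks.

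**3. Gap to five half-lives.**
- At the stated half-life: 5 × 21 = 105 days = 15 weeks, and 15 − 6 = 9 weeks short.
- If a 40% protein loss is assumed to raise clearance by 1/0.6 with volume unchanged, the half-life is 21 × 0.6 = 12.6 days. Then 5 × 12.6 = 63 days = 9 weeks, and 9 − 6 = 3 weeks short.

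**4. Fraction of the terminal-phase level left at 42 days**, 0.5^(42/half-life):
- 21 days (stated): 0.25
- 14 days (assumed): 0.125
- 28 days (assumed): 0.354
- 12.6 days (assumed leakage case): 0.099

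If Visit 9 falls 7 days early, the stated half-life leaves 0.5^(35/21) = 0.31.

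**5. Approximate serum level at Visit 9.** Assume mono-exponential decline and that the predicted minimum holds at Week 12, two weeks after the last dose. Visit 9 is 28 days later.

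| Level at Week 12 | Half-life 21 d | Half-life 12.6 d |
|---|---|---|
| 96 µg/mL | 96 × 0.5^(28/21) = 38.1 | 96 × 0.5^(28/12.6) = 20.6 |
| 59 µg/mL | 59 × 0.5^(28/21) = 23.4 | 59 × 0.5^(28/12.6) = 12.6 |

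All four exceed 10 µg/mL.

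**6. Time from last dose to 10 µg/mL, starting at 96 µg/mL at Week 12.** 14 + 21 × log2(9.6) = 82.5 days = 11.8 weeks; 14 + 12.6 × log2(9.6) = 55.1 days = 7.9 weeks.

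**The case against.** The 6-month windows were written for other purposes. Exclusion criterion 9 is about intent and Section 21.6.3 about reporting; neither sets a contraception period, and surveillance can reasonably outlast prevention. For men, the only 6-month text is the reporting rule. That stands, and it is why this is a mismatch of windows and not a contradiction: all three rules can be followed together.

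On pharmacology, the shortfall is smaller than 20 weeks. Five half-lives give a gap of 3 to 9 weeks, and 6 months is 8.7 stated half-lives (about 0.2% remaining). This is fair and is the reason to leave room for a justified washout-based period. It does not rescue 6 weeks, which falls short of either version.

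The benchmarks are borrowed. The 10 µg/mL figure relates to efficacy, not fetal safety, and exclusion criterion 10 concerns drugs taken before randomization. The serum projections are also approximate. Section 18.3 says its predictions already allow for intestinal leakage, so pairing 96 µg/mL with the unadjusted 21-day half-life mixes scenarios. The consistent leakage pairing gives about 21 µg/mL at Visit 9, with 10 µg/mL reached at 7.9 weeks, about 2 weeks after that visit. The 59 µg/mL row is a stress case, since that figure appears to describe the time before the Week 1 dose. These points limit how far the projections can be pressed; the mismatch of windows depends on none of them.

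Finally, a rationale for 6 weeks may lie in the redacted toxicology and PK sections, the Investigator's Brochure or the consent form, none of which could be read. One third of subjects (8 of 24) receive placebo, but blinding hides which. Subjects who enter the bridging program or extension will come under separate protocols; the others will not.

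**Conclusion.** The concern holds. Required contraception ends 6 weeks after the last dose, about 20 weeks before the protocol's two 6-month pregnancy windows close. It is also 9 weeks short of five half-lives at the stated half-life, or 3 weeks short under the assumed leakage adjustment. The 20-week figure rests only on the protocol's dates. The statement that drug is probably still above 10 µg/mL at Visit 9 rests on mono-exponential decline and on the predicted minimum holding at Week 12.

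Exclusion criterion 9 reduces the exposure for women by removing planned pregnancies. What remains is unplanned pregnancy or a change of intention in women, and partner pregnancy for men. How dangerous fetal exposure would be cannot be judged from these documents. This should be corrected: the possible harm is serious, the 6-month figure is the sponsor's own, and the text available gives no reason for 6 weeks.

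**What to change.** - In inclusion criterion 3, in both the synopsis and Section 9.1, extend the contraception requirement to 6 months after the last dose for females of childbearing potential and for males.
- If the clinical team prefers a shorter washout-based period, such as five half-lives (about 15 weeks), state it with its rationale and apply it consistently.
- In exclusion criterion 9 of Section 9.2, change 'of' to 'or'.
- Check that the consent form gives the same period; it was not available for this review.

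The cost is protocol wording and a consent check. Participants, including those on placebo because of the blind, carry up to about 20 more weeks of contraception. No visits or procedures are added.

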9.2 EXCLUSION CRITERIA

Subjects will be excluded from participation in the study if there is evidence of any of the following, at screening and Visit 1:

1. Diagnosis of RCD-I or EATL (excluded by the site's standard imaging techniques for this purpose).
2. Presence of any of the following related to infection:
 - a) Active acute infection requiring systemic antibiotic, parenteral antifungal, or systemic antiviral treatments
 - b) Severe infection within the 3 months prior to screening
 - c) History of tuberculosis (TB)
 - d) Positive IGRA test at screening OR known recent exposure (within 6 months prior to screening) to a patient with active TB (subject can be enrolled if he or she has been successfully treated with appropriate chemoprophylaxis).
 - e) History within the 3 years prior to screening of an opportunistic infection typical of those seen in immunocompromised subjects (e.g., systemic candida infection, or systemic fungal infection).
3. Current diagnosis or history of cancer in the past 5 years, except RCD-II, successfully treated basal cell or squamous cell carcinoma, cervical carcinoma-in-situ, or early stage prostate cancer.
4. History or presence of clinically significant disease that in the opinion of the Investigator, would confound the subject's participation and follow-up in the clinical trial or put the subject at unnecessary risk including but not limited to:

- a) Cardiovascular disease [e.g., uncontrolled hypertension (office systolic blood pressure [BP] equal to or greater than 180 mmHg or office diastolic BP equal to or greater than 110 mm/Hg), unstable angina, congestive heart failure worse than NYHA Class II, coronary angioplasty or myocardial infarction within the last 6 months, uncontrolled atrial or ventricular cardiac arrhythmias clinically significant pleural or pericardial effusion or ascites)
 - b) Pulmonary disease (e.g., severe chronic pulmonary disease)
 - c) Renal, hematological, gastrointestinal, endocrine (e.g., poorly controlled diabetes), immunologic, dermatologic, neurological, or psychiatric disease
5. History of significant immune suppression:
 - a) BMT or cladribine therapy less than 6 months prior to baseline.
 - b) Potent systemic immune suppressants (e.g., azathioprine) within the 3 months prior to baseline.
 6. History of alcohol or drug abuse that would interfere with the ability to comply with the study protocol.
 7. History of clinically significant hypersensitivity to the study drug or any related drugs or to any of the excipients.
 8. Positive Hep B, Hep C, or HIV test results at the time of screening.
 9. Females who are pregnant or planning to become pregnant during the study participation period of 6 months after last dose, or are currently breastfeeding.
 10. Participation in another investigational drug or device study or treatment with an investigational drug within 30 days or 5 half-lives, whichever is longer, prior to randomization.
 11. Any additional reason, which in the opinion of the Investigator, would prevent the subject from safely participating in the study or complying with protocol requirements.

10 CONCOMITANT MEDICATIONS

10.1 PROHIBITED MEDICATIONS

The following medications are not allowed at the time of randomization (Visit 1, Week 0/Day 0) or throughout the study:

- Systemic or intestinal immune suppressants, excluding steroids at a maximum dose of 20 mg of prednisone, prednisolone or equivalent per day and/or oral budesonide at a maximum dose of 9 mg/day. Systemic immune suppressants should not be used within the 3 months prior to randomization. Inhaled steroids for respiratory diseases such as asthma, and topical steroids are permitted.
- Chronic or continuous oral and IV antibiotics (>2 weeks use). Topical antibiotic use is allowed.

- Systemic antivirals
- Parenteral antifungals
- Anticoagulants in the week prior to the protocol-indicated biopsies (alternatively, local guidelines for the prevention of bleeding during endoscopy can be followed).
- Live vaccines.
- Investigational drugs or devices.

Note: After randomization, use of any of these medications is permitted if required for treatment of an AE. These medications may be started following discussion with and approval of the medical monitor. If discussion is not possible and approval has not been obtained prior to starting these medications, the situation should be discussed with the medical monitor promptly after treatment has been instituted to avoid classification as a protocol deviation. In the absence of discussion with the medical monitor, as described, starting these medications following randomization will be classified as a protocol deviation. If the prohibited concomitant medication is determined to interfere with the results of the study, withdrawal of the subject shall occur at the discretion of the Investigator or the sponsor.

Note: It is permitted to administer albumin if needed for the purpose of correcting excessive hypoalbuminemia in the context of protein-losing enteropathy, at the Investigator's discretion.

